2.3 Patient disposition, demographics and other baseline characteristics

The Full Analysis Set (FAS) will be used for all baseline and demographic summaries and listings unless otherwise specified. No inferential statistics will be provided.

The analysis for basic demographic and baseline characteristics, diagnosis and extent of SAA, medical history, and analysis sets will not be reproduced for final CSR. Only hematological parameter counts at baseline will be reproduced for final CSR since some missing values of Reticulocyte absolute count will be derived from Reticulocyte count % * RBC count in SI unit (10E12/L) * 10.

2.3.1 Basic demographic and baseline characteristics

All demographic data will be summarized and listed. Categorical data (e.g. gender, age groups: 18-64 years, ≥ 65 years, others as applicable) will be summarized by frequency counts and percentages; the number and percentage of patients with missing data will be provided. Continuous data (e.g. age, weight, height) will be summarized by descriptive statistics (N, mean, median, standard deviation, minimum and maximum).

Haematological parameters at the assessment of patients eligibility including platelet count, haemoglobin, absolute neutrophils count (ANC) and absolute reticulocytes count (ARC) will be summarized by descriptive statistics (N, mean, median, standard deviation, minimum and maximum). RBC and Platelet Transfusion (Independence and Dependence), and G-CSF injection required (Yes/No) at baseline will be summarized by frequency counts and percentages.

The following other baseline characteristics will be summarized by frequency counts and percentages:

- Relapsed patients, refractory patients and patients who achieved PR after the last course of IST with platelet count $<30 \times 10^9 / L$,
- Concomitant use of CsA and anabolic steroids at baseline: Yes, No,
- Prior ATG/ALG Therapies: Yes, No.

2.3.2 Diagnosis and extent of SAA

Summary statistics will be tabulated for diagnosis and extent of SAA. This analysis will include the following if they are available: stage at initial diagnosis, time since initial diagnosis, time

from initial diagnosis to first recurrence/progression (in months), and time since most recent relapse/progression to first dose (in months).

2.3.3 Medical history

Medical history and baseline symptoms (current medical conditions) will be summarized separately and listed. The summaries will be presented by primary system organ class (SOC), preferred term (PT) and treatment arm. Medical history and current medical conditions will be coded using the Medical Dictionary for Regulatory Activities (MedDRA) terminology. The MedDRA version used for reporting will be specified in the CSR and as a footnote in the applicable tables/listings.

2.3.4 Other

All other data collected at baseline will be listed.

2.3.5 Patient disposition

The number (%) of treated patients included in the FAS will be presented. The number (%) of screened and not-treated patients and the reasons for screening failure will also be displayed.

The following summaries will be provided (with % based on the total number of FAS patients):

- Number (%) of patients who are still on-treatment;
- Number (%) of patients who completed the 26 weeks treatment phase;
- Number (%) of patients who discontinued earlier than 26 weeks ;
- Primary reason for the 26 weeks treatment phase discontinuation;
- Number (%) of patients who have entered the 52 weeks treatment phase;
- Number (%) of patients who completed the 52 weeks treatment phase;
- Number (%) of patients who discontinued between 26 and 52 weeks;
- Primary reason for the 52 weeks treatment phase discontinuation;
- Number (%) of patients who have entered the extension treatment phase;
- Number (%) of patients who are still on extension treatment phase;
- Number (%) of patients who have completed the study
- Number (%) of patients who have discontinued the study
- Primary reason for discontinuation of the study

2.3.6 Protocol deviations

The number (%) of patients in the FAS with any protocol deviation will be tabulated by deviation category (as specified in the study Data Handling Plan) overall for the FAS. All protocol deviations will be listed.

In addition to the pre-defined standard PD terms, Novartis has also defined new protocol deviations and the corresponding relationship to the COVID-19 pandemic. The protocol deviations related to the COVID-19 pandemic will be summarized.

2.3.7 Analysis sets

The number (%) of patients in each analysis set (defined in [Section 2.3](#)) will be summarized.

2.4 Treatments (study treatment, rescue medication, concomitant therapies, compliance)

2.4.1 Study treatment / compliance

Duration of exposure, actual cumulative dose, dose intensity (DI) and relative dose intensity (RDI) will be summarized. Duration of exposure will be calculated by two methods, the first one is actual duration of exposure which is exclusive of interruption of eltrombopag. The second one is duration of exposure which is inclusive of interruption due to good response. Duration of exposure will be categorized into time intervals; frequency counts and percentages will be presented for the number(%) of subjects in each interval. The number (%) of subjects who have dose reductions or interruptions, and the reasons, will be summarized.

Subject level listings of all doses administered on treatment along with dose change reasons will be produced.

The safety set will be used for all summaries and listings of study treatment.

Duration of exposure to study treatment

Duration of exposure to study treatment is considered by taking into account the duration of exposure to the investigational drug:

Duration of exposure to study treatment (days) = (last date of exposure to study treatment) – (date of first administration of study treatment) + 1.

The last date of exposure to study treatment is the latest of the last dates of exposure to investigational drug. For those patients still on treatment at cutoff date, the cutoff date will be imputed as the last date of exposure to study treatment.

Summary of duration of exposure of study treatment will include categorical summaries (i.e. < 13 weeks, 13 weeks to 26 weeks, > 26 weeks to 52 weeks, > 52 weeks) and continuous summaries (i.e. mean, standard deviation etc.).

Cumulative dose

Cumulative dose is defined as the total dose given during the study treatment exposure.

The **planned cumulative dose** for a study treatment component refers to the total planned dose as per the protocol up to the last date of investigational drug administration. The planned dose in this study equals to prescribed dose in Study Treatment eCRF.

The **actual cumulative dose** refers to the total actual dose administered, over the duration for which the subject is on the study treatment as documented in Study Treatment eCRF.

For patients who did not take any drug the cumulative dose is by definition equal to zero.

Dose intensity and relative dose intensity

Dose intensity (DI) for patients with non-zero duration of exposure is defined as follows:

DI (mg/day) = Actual Cumulative dose (mg) / Duration of exposure (day)

For patients who did not take any drug the DI is by definition equal to zero.

Planned dose intensity (PDI) is defined as follows:

PDI (mg/day) = Planned Cumulative dose (mg) / Duration of exposure (day).

Relative dose intensity (RDI) is defined as follows:

RDI = DI (mg/day) / PDI (mg/day).

DI and RDI will be summarized by descriptive statistics (N, mean, median, standard deviation, minimum and maximum) for the study treatment. DI, RDI and cumulative dose will be listed together with the appropriate patient characteristics. RDI will be categorized as follows: <=75%, >75 - 90%, >90 - 110%, >110%.

Dose changes and interruptions

The number of subjects who have dose changes, interruptions, and the reasons will be summarized.

‘Dose changed’ and ‘Dose interrupted’ fields from the Study Treatment CRF pages will be used to determine the dose changed and dose interruptions.

The corresponding fields ‘Reason for dose changed/dose interrupted’ will be used to summarize the reasons.

A dose change is either ‘change in prescribed dose level’ or ‘dosing error’ where actual dose administered is different from the prescribed dose.

For the purpose of summarizing interruptions and reasons, in case multiple entries for interruption that are entered on consecutive days with different reasons will be counted as separate interruptions. However, if the reason is the same in this mentioned multiple entries on consecutive days, then it will be counted as one interruption.

2.4.2 Prior, concomitant and post therapies

Concomitant therapies will be coded using the WHO Drug Reference List dictionary that employs the WHO Anatomical Therapeutic Chemical (ATC) classification system and summarized by lowest ATC class and preferred term using frequency counts and percentages. These summaries will include therapies starting on or after the start of study treatment but no later than 30 days after last dose of study treatment or therapies starting prior to the start of study treatment and continuing after the start of study treatment.

Concomitant medications that have the potential to impact efficacy results (e.g. CsA, anabolic steroids and G-CSF) will be identified prior to database lock. Separate summaries of these concomitant medications will be produced using the FAS.

All therapies will be listed. Any therapy starting and ending prior to the start of study treatment or starting more than 30 days after the last date of study treatment will be flagged in the listing as prior or post therapies respectively. Those starting or continuing on or after the start date of study treatment and up to 30 days after the last date of study treatment will be flagged as concomitant therapies in the listing. The safety set will be used for all therapies tables.

The analysis for prior medication will not be reproduced at updated analysis and final analysis.

2.5 Analysis of the primary objective

The primary objective of the study is to assess the efficacy of eltrombopag treatment at 6 months in Chinese subjects with a previous diagnosis of severe aplastic anemia and who had insufficient response following at least one treatment course in the period time of > 6 months of immunosuppression with a regimen containing anti-thymocyte globulin (ATG), anti-lymphocyte globulin (ALG), and/or cyclophosphamide, or alemtuzumab, and who are ineligible for HSCT or a suitable donor is not available.

2.5.1 Primary endpoint

The primary endpoint is the hematologic response rate at Week 26, which is defined as the proportion of all subjects who meet any of the International Working Group (IWG) criteria at Week 26 shown in the table below. The primary endpoint will be based on the investigator assessment of response.

The analysis for primary endpoint as well as related supplementary and supportive analysis will not be reproduced for final CSR.

The primary analysis will be based on FAS and will include all data observed up-to the cut-off date.

Table 2-2 IWG criteria for Primary Endpoint

Assessment Item	Baseline transfusion status	Response Criteria
Platelet count	Platelet transfusion independent	Transfusion independent ⁽¹⁾ and increase from baseline by $20 \times 10^9/L$ or more
	Platelet transfusion dependent	No platelet transfusion requirement for 8 weeks
Hemoglobin	RBC transfusion independent	When the baseline hemoglobin level is < 90 g/L: transfusion independent and increase from baseline by 15 g/L or more
	RBC transfusion dependent	A decrease of at least 4 units in RBC transfusions in the post-treatment 8-week period (1 unit = RBC derived from 200 mL blood) Or no RBC transfusion requirement for 8 weeks (less than 4 units RBC in 8-week period at Baseline)

Assessment Item	Baseline transfusion status	Response Criteria
Neutrophil count	NA	(In the absence of G-CSF taken within 21 days preceding the blood sample collection) Increase from baseline by $0.5 \times 10^9/L$ or more, or (if $< 0.5 \times 10^9/L$ at baseline) increase by 100% or more

Note: No platelet/RBC transfusion requirement for 8 weeks means there is no any platelet/RBC transfusion received by patients during (Visit date-56 days) until Visit date. This definition also applies to Week 13 and Week 52.

(1) Transfusion independent means subjects did not receive platelet transfusion in the 4 weeks before Visit date.

During regular hematologic assessment, the exclusion period of transfusion and G-CSF are detailed below:

Platelet transfusion: 7 days preceding the assessment of platelet count

RBC transfusion: 14 days preceding the assessment of hemoglobin

G-CSF: 21 days preceding the assessment of neutrophil count

Definition of baseline Platelet Transfusion Independence/Dependence and platelet count

Baseline platelet transfusion independence/dependence and platelet count are defined as:

- For platelet transfusion independent subjects that did not receive platelet transfusions in the 4 weeks before Day 1(include Day 1): The average of the most recent 2 platelet counts before Day 1(include Day 1).
- For transfusion dependent subjects that received one or more platelet transfusions in the 4 weeks before Day 1(include Day 1): The average of the most recent 2 platelet counts before Day 1 (excluding platelet counts within 6 days * following a platelet transfusion). If all platelet counts available are within 6 days* following a platelet transfusion, the lowest platelet count prior to initiation of study drug will be used as the baseline platelet count.

*: e.g. When a platelet transfusion was done on December 2nd (Monday), the platelet count will become usable from December 9th (Monday).

Definition of baseline RBC Transfusion Independence/Dependence and hemoglobin value

Baseline RBC transfusion independence/dependence and hemoglobin value are defined as:

- For RBC transfusion independent subjects that did not receive RBC transfusions in the 8 weeks before Day 1(include Day 1): The most recent hemoglobin value before Day 1(include Day 1).
- For RBC transfusion dependent subjects that received one or more RBC transfusions in the 8 weeks before Day 1(include Day 1): The last hemoglobin value prior to the most recent RBC transfusion. If no values exist prior to a RBC transfusion, the lowest value before Day 1(include Day 1) will be used.

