2.1.3 General definitions

Study drug and Study treatment

The study drug/study treatments for this study is eltrombopag (ETB115).

Eltrombopag will be supplied as film-coated tablets (25 mg) provided either as commercial packages locally.

Date of first administration of study treatment

The date of first administration of study treatment will be derived as the first date when a nonzero dose of study treatment is administered and recorded on the appropriate CRF.

Date of last administration of study treatment

The date of last administration of study treatment will be derived as the last date when a nonzero dose of study treatment is administered and recorded on the appropriate CRF. For those patients still on treatment at cutoff date, the cutoff date will be imputed as the date of last administration of study treatment.

Study day

The study day, describes the day of the event or assessment date, relative to the reference start date.

The study day is defined as:

- The date of the event (visit date, onset date of an event, assessment date etc.) – reference start date + 1 if event is on or after the reference start date;
- The date of the event (visit date, onset date of an event, assessment date etc.) – reference start date if event precedes the reference start date.

The reference date for all assessments (safety, efficacy, pk, etc) is the date of first administration of study treatment as defined above. The study day will be displayed in the data listings.

Time unit

A year length is defined as 365.25 days. A month length is 30.4375 days (365.25/12). If duration is reported in months, duration in days will be divided by 30.4375. If duration is reported in years, duration in days will be divided by 365.25.

Baseline

For safety and efficacy evaluations, the last available assessment on or before the date of first administration of study treatment is defined as “baseline” assessment. If patients have no value as defined above, the baseline result will be missing.

On-treatment assessment/event and observation periods

The overall observation period will be divided into three mutually exclusive segments:

1. ***pre-treatment period***: from day of patient's informed consent to the day before first administration of study treatment
2. ***on-treatment period***: from date of first administration of study treatment to 30 days after date of last actual administration of study treatment (including start and stop date)

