2.5.2 Statistical hypothesis, model, and method of analysis

The proportion of the hematological response will be summarized using point estimates and 90% exact (Clopper-Pearson) confidence intervals.

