2.14 Interim analysis

There will be no formal interim analysis planned in this study.

3 Sample size calculation

As this is a bridging study to support China registration, an estimation strategy rather than formal hypothesis testing will be pursued. Approximately 20 subjects will be enrolled into the study based on the feasibility rather than statistical considerations. This number of subjects is considered appropriate to assess the efficacy and safety of eltrombopag in Chinese patients.

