3.1 Primary analysis

The hematologic response rate at Week 24 in the pivotal study of NIH-09-H-0154 was 40%. Assuming a same response rate (40%) in Chinese subjects, the 90% confidence interval of the hematological response rate with a total of 20 subjects will be (21.7%, 60.6%).

Below table shows the 90% CIs for various observed response rate. The maximum half-width of the 90% CIs is 19.8%.

Table 3-1 90% CIs for various observed response rate

Sample size	# of responders	Hematologic response rate (%)	90% CI (%)
20	4	20	(7.1, 40.1)
20	6	30	(14.0, 50.8)
20	8	40	(21.7, 60.6)

Sample size	# of responders	Hematologic response rate (%)	90% CI (%)
20	10	50	(30.2, 69.8)

The 12 evaluable subjects for intensive PK sampling was chosen based on feasibility and practical considerationzs to assist in characterizing the PK of eltrombopag in Chinese subjects.

4 Change to protocol specified analyses

No change from protocol specified analysis was made.

5 Appendix

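### No neutrophil baseline is defined: the SAP's programmed analyses fall back on a single last count with no G-CSF condition, although the response count must be G-CSF-free for 21 days

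*SAP*

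**What the plan says.** **Response side.** SAP Table 2-2 (Protocol Table 8-2 is the same) counts a neutrophil response when the count rises by at least 0.5 × 10⁹/L, or by at least 100% if baseline is below 0.5 × 10⁹/L. The condition is "In the absence of G-CSF taken within 21 days preceding the blood sample collection". The list of exclusion periods under the table, introduced as applying at regular hematologic assessments, repeats it: "G-CSF: 21 days preceding the assessment of neutrophil count".

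**Baseline side.** SAP 2.5.1 and Protocol 8.3.1 then define two baselines.
- Platelets: "The average of the most recent 2 platelet counts before Day 1". In transfusion-dependent subjects, counts within 6 days after a transfusion are left out.
- Hemoglobin: a single value, taken before the most recent transfusion in RBC-dependent subjects.

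No neutrophil baseline follows. What remains is the general rule in SAP 2.1.3, which takes as baseline "For safety and efficacy evaluations, the last available assessment on or before the date of first administration of study treatment", with no G-CSF condition.

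**Selection of counts.** SAP 2.1.3 (Table 2-1) uses one assessment per visit window. No confirmation is required.

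**G-CSF is expected.** SAP 2.3.1 states that "G-CSF injection required (Yes/No) at baseline will be summarized by frequency counts and percentages". SAP 2.4.2 names G-CSF among the concomitant drugs that could affect efficacy results.

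**Who decides response.** The primary endpoint is the investigator's assessment. SAP 2.5.4 adds a programmed response whose named sources are laboratory results and transfusion records; G-CSF records are not named.

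**The concern.** The two ends of the neutrophil comparison are not held to the same stated standard. A count raised by G-CSF may serve as the baseline, while the count compared with it must be free of G-CSF for 21 days. Some of the rise that the criterion asks for may then already be in the baseline, so a true responder is missed.

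Single-count noise works the other way. At counts below 0.5 × 10⁹/L a doubling is a small absolute change, and one unconfirmed doubling is enough.

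Response in any one lineage makes a subject a responder, and the study has about 20 subjects, so each reclassification in a response analysis moves the rate by 5 percentage points. The same baseline is needed for the neutrophil change summaries and for the neutrophil duration-of-response curve, where relapse means no longer meeting the criteria. SAP 2.7.1 still produces both for the final report.

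**Working it through.** **1. The plan's own precision figures.** Inputs: n = 20, from SAP Section 3 ("Approximately 20 subjects will be enrolled into the study based on the feasibility rather than statistical considerations"), and SAP 2.5.2 ("90% exact (Clopper-Pearson) confidence intervals"). For x responders the limits are the 5% quantile of Beta(x, 21 − x) and the 95% quantile of Beta(x + 1, 20 − x).
- 8/20 gives 21.7% to 60.6%, as stated in SAP 3.1. The other rows of Table 3-1 and the maximum half-width of 19.8 points also reproduce.
- One subject gained: 9/20 = 45%, 25.9% to 65.3%.
- One subject lost: 7/20 = 35%, 17.7% to 55.8%.

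The documents give no figure for the neutrophil route. Steps 2 to 4 therefore rest on assumptions, shown as ranges.

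**2. G-CSF in the baseline.** Required count = min(baseline + 0.5, 2 × baseline) if baseline is below 0.5, otherwise baseline + 0.5 (all × 10⁹/L). Assume a true count of 0.2.

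| Assumed G-CSF effect | Recorded baseline | Required count | Multiple of true count |
|---|---|---|---|
| none | 0.2 | 0.4 | 2.0 |
| 2-fold | 0.4 | 0.8 | 4.0 |
| 3-fold | 0.6 | 1.1 | 5.5 |

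At 3-fold the 100% route is closed, because the recorded baseline is no longer below 0.5. The direction is toward non-response, and only subjects with G-CSF shortly before the baseline sample are affected.

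**3. Chance doubling.** Assume log-normal counts with no true change. Then s = √ln(1 + CV²), and for one count against one count P(ratio ≥ 2) = P(Z ≥ ln 2 / (s√2)). At CV 35%, for example, s = 0.340, z = 0.693 / 0.481 = 1.44 and P = 7.5%. The last two columns are simulated with the Table 2-2 neutrophil rule at a true count of 0.2.

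| Within-subject CV (assumed) | One against one | Two-count baseline | Two-count baseline, rise also held at a second count |
|---|---|---|---|
| 20% | 0.7% | 0.2% | 0.0% |
| 30% | 4.8% | 2.4% | 0.2% |
| 35% | 7.5% | 4.2% | 0.6% |
| 40% | 10.2% | 6.2% | 1.1% |
| 50% | 15.0% | 10% | 2.4% |

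**4. From per-subject rate to overall rate.** Only subjects not responding by another lineage can be reclassified. If 40% respond by other routes and the remaining 60% all have no true neutrophil change and a baseline below 0.5:
- CV 20%: 0.40 + 0.60 × 0.007 = 40.4%
- CV 50%: 0.40 + 0.60 × 0.150 = 49.0%

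Subjects who also have G-CSF in the baseline pull the other way. The documents do not say how many there are, so no net figure can be given.

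**5. A limit on any fallback.** Taking the lowest pre-dose count selects downward. With two pre-dose counts and no G-CSF effect, chance response under that rule is 12.8% at CV 35% and 24.2% at CV 50%, against 7.5% and 15.0% for a single last count. A fallback of this kind needs to be visible in the results.

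**The case against.** **The text is silent; it does not exempt baseline.** The G-CSF condition stands ahead of both increase-from-baseline clauses, and the 21-day line could be read to cover the baseline sample. This stands as a possible reading. Against it, the list is headed as applying at regular assessments, and the other two lineages have separate baseline rules. Two tenable readings are a reason to settle the matter in words.

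**The general baseline rule does not govern the primary endpoint.** A reader might infer that the Week 26 primary rate is biased by it. The documents do not support that. Response is the investigator's assessment, and neither document tells investigators which neutrophil baseline to use. The rule in SAP 2.1.3 reaches the derived response and the neutrophil change analyses. It reaches the duration curve only as far as that is programmed, which the SAP does not say.

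**Noise is not special to neutrophils.** This is right. Hemoglobin in RBC-independent subjects is also one value against one value.

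**Much is already visible.** The seven-combination table in SAP 2.5.5 isolates neutrophil-only responders, and baseline G-CSF use is tabulated. The two are not crossed, however, and baseline G-CSF use is not among the subgroups in SAP 2.2.1.

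**Timing.** This SAP version serves the final analysis and does not rerun the primary endpoint or its supplementary analyses. That stands, and it limits what a change can still do prospectively to neutrophil change and duration of response.

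**Conclusion.** The gap is real and modest. Neither document defines a neutrophil baseline, and in the programmed analyses the stated default can set a G-CSF-raised single count against a G-CSF-free one.

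Its size rests on assumptions. For a subject with no true change and a baseline below 0.5 × 10⁹/L, the chance of a false neutrophil response is about 1% to 15% at a within-subject CV of 20% to 50%. For a subject with a true count of 0.2 and a two- to three-fold G-CSF effect at baseline, the required rise is 4 to 5.5 times the true count instead of 2. The CVs, fold effects and true count are not in the documents, and neither is the number of subjects given G-CSF before baseline.

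Because the two effects oppose each other, it cannot be said that the response rate is overstated or understated. The confidence-interval table is unaffected.

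**What to change.** 1. In SAP 2.5.1, define the neutrophil baseline as the mean of the last two counts up to Day 1 that are not within 21 days after G-CSF, or the single count if only one qualifies. If none qualifies, use the lowest pre-dose count, as in the platelet rule, flag the subject, and show results with and without flagged subjects.
2. In SAP 2.5.4, name G-CSF records as a source. Apply the definition to the derived response, neutrophil change and neutrophil duration of response.
3. Add one supplementary row counting neutrophil-only responders whose rise holds at the next scheduled count. Show separately those with no later count before the cut-off, since SAP 2.1.1 bars later data.
4. Report neutrophil-only responders by baseline G-CSF use.
5. Leave the response criteria and the investigator-assessed primary analysis unchanged. Label as post hoc anything applied to the completed Week 26 analysis.

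**Cost.** SAP wording, a flag and a few table rows; no new data collection. A few derived classifications may differ from the investigator's. Protocol 6.2.1 records supportive therapy other than transfusions from the screening visit, which can be fewer than 21 days before the baseline sample, so G-CSF given before screening may not be recorded; the table should carry a note to that effect.
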